Study to Assess Oropharyngeal Carriage of *N. Meningitidis* in South Australian School Leavers.

Clinicaltrials.gov: NCT03419533

Protocol V5, 7th November 2017

PHASE 2: AN OBSERVATIONAL CROSS SECTIONAL STUDY TO ASSESS NASOPHARYNGEAL CARRIAGE OF *N. MENINGITIDIS* IN SOUTH AUSTRALIAN UNIVERSITY STUDENTS AND SCHOOL LEAVERS

PHASE 2 (STUDY PART 2 AND STUDY PART 3) PROTOCOL SUMMARY		
Title:	South Australian Men B vaccine herd immunity study.	
	Study Part 2: Pilot observational longitudinal study to assess nasopharyngeal carriage of Neisseria meningitidis in South Australian university students	
	Study Part 3: An observational cross sectional study to assess nasopharyngeal carriage of Neisseria meningitidis in South Australian school leavers.	
Précis:	To estimate the prevalence of N. meningitides in first year university students and school leavers in South Australia posterior oro-pharyngeal swabs will be obtained prior to and post implementation of the school immunisation program (Phase 1). Potential risk factors will be assessed along with a comparison of carriage prevalence in vaccinated and unvaccinatedparticipants. Carriage will be estimated at baseline (2017) and in 2018, 2019 and potentially additionally in 2020 if funding available (post implementation of the school immunisation program (Phase 1).	
Objectives:	Study Part 2: 2017 Pilot Longitudinal Carriage Study	
	Primary Objective	
	• Estimate the carriage prevalence of all genogroups of N. meningitidis in South Australian first year university students.	
	Secondary Objectives	
	• Estimate the carriage prevalence of N. meningitidis genogroups causing disease (A , B , C , W , X , Y) in South Australian first year university students.	
	• Identify characteristics associated with carriage prevalence of all N. meningitidis genogroups in South Australian first year university students.	
	• Estimate the change in carriage prevalence of all genogroups of N . meningitidis in South Australian first year university students at baseline (first week of university) and 3 months later Estimate any difference in PCR positivity after freezing of the sample at 6, 16 and 48 hours post collection.Estimate any difference in positivity of isolates determined by culture after freezing of samples at 6, 16 and 48 hours post collection	
	Study Part 3: 2018 /2019 /2020 Cross-sectional carriage study	
	Primary Objective	

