6.1 STUDY PROCEDURES/EVALUATIONS

6.1.1 STUDY SPECIFIC PROCEDURES

Pharyngeal swabs will be collected from participants using a standard operating procedure (SOP) to ensure consistent and optimal collection and handling of swabs. A swab will be placed at the back of the throat and swept across the posterior pharynx and withdrawn. Laboratory procedures/evaluations are described in Phase 1.

Study part 2 will additionally measure any difference in PCR positivity for *N. meningitidis* following freezing at 6 hours post collection and 16 and 48 hours post collection. This will assist in validating laboratory procedures for the RCT study. Once the sample has been received by SA Pathology each sample will be aliquoted into three cryovials and frozen at three different timepoints (6 hours, 16 hours, and 48 hours) following collection time.

Specimen and laboratory flow diagram for study part 2

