4. DESCRIPTIVE STATISTICS

4.1 Baseline characteristics

A descriptive comparison of the 2018 and 2019 groups will be conducted on the baseline characteristics presented in the following table.

Baseline characteristic	Categories
Age - years	-

Baseline characteristic	Categories
Sex	Female Male
Participation in the High School B Part of It Meningococcal Study	Yes No Unsure
Meningococcal B vaccine status	Yes (<= 12 months since dose 2) Yes (> 12 months since dose 2) Partial (only one dose) No
Meningococcal ACWY vaccine status	Yes (<= 12 months) Yes (> 12 months) No
Working status	Full time work Part time work Part time work + study Full time student Not working or studying Other
Smoking	Yes No
Cigarettes / day	-
Smoked e-cigarette in the last week	Yes No
Number of times smoked an e-cigarettes in the last week	-
Smoked water pipe in the last week	Yes No
Number of times smoked a water pipe in the last week	-
Number of persons/room	0 to 1

Baseline characteristic	Categories
	>1 to ≤2 >2
Ethnicity	Aboriginal Torres Strait Islander Caucasian Asian Middle East African Pacific Islander Other
Other smokers at home	Yes No
Antibiotics	None Stopped last month Stopped last week Yes, currently taking
Mouth wash used in the last month	Yes No
Times used mouth wash in last month	-
Number of days out in last week	-
Drank alcohol in the last month	Yes No
Number of days drank alcohol in last month	-
In those that drank in the last month, number of drinks on a typical drinking day	-
Days drank in the last month X typical drinking day	-
Number of people kissed in the last week	-
In current relationship	Yes No
Is partner a smoker	Yes

Baseline characteristic	Categories
	No N/A

Means and standard deviations will be reported for continuous variables, while frequencies and percentages will be reported for categorical variables.

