5. SAMPLE SIZE ESTIMATION

Assuming the carriage prevalence of disease associated genogroups of *N. meningitidis* (A, B, C, W, X, Y) in school leavers in 2018 is 8%, a sample size of 4,096 students per year will provide 80% power to detect a 20% relative reduction in carriage prevalence between 2018 and 2019 (two tailed alpha = 0.05).

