6.2 Adjustment

Adjustment will be made for risk factors that had a two-tailed p-value < 0.05 in the multivariable model for baseline disease-causing carriage in the High School B Part of It RCT (see <https://clinicaltrials.gov/ct2/show/NCT03089086> for description of study). These include current cold or sore throat (no, yes), smoking cigarettes (no, yes), smoking water pipes (no, yes), days out at a pub/club in last week (0, 1 or more), people kissed in last week (0, 1 or more), and ethnicity (Caucasian, Asian, Aboriginal or Torres Strait Islander, Other). Adjustment will also be made for alcohol consumption in the last month (no, yes), as this emerged as an important risk factor

for disease-causing carriage in a preliminary analysis of 2018 School Leaver data. Previous vaccination with MenACWY (no, yes) and participation in the High School B Part of It RCT (no, yes) will also be considered for inclusion in the adjusted model. In order to address each hypothesis, both unadjusted and adjusted analyses will be performed, with primary conclusions to be based on the results of adjusted analyses. No adjustment will be made for risk factors in the analysis of carriage of genogroups A, C, W and X, as only small numbers of cases are expected to be detected.

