6.4 Primary Outcome

6.4.1 Carriage prevalence of disease causing genogroups of *N. meningitidis* (A, B, C, W, X, Y) in school leavers in 2018 compared to 2019

Outcome: Binary outcome based on the presence of at least one disease-causing genogroup of *N. meningitidis* (A, B, C, W, X, Y) by polymerase chain reaction (PCR).

Effect: Odds ratio for disease-causing genogroups of *N. meningitidis* (2018 vs 2019).

Analysis: Test for a difference using logistic regression. Adjustment will be conducted as described in 6.2.

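### Must SAP 6.2 settle in advance whether the primary 2018 v 2019 odds ratio is adjusted for RCT participation?

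*SAP*

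**What the plan says.** SAP 6.4.1 defines the primary result as an odds ratio for disease-causing genogroups, 2018 against 2019, from logistic regression adjusted as in SAP 6.2. Section 6.2 fixes seven covariates: cold or sore throat, cigarettes, water pipes, pub or club visits, kissing, ethnicity and alcohol. It leaves two open. One is MenACWY vaccination. For the other, "participation in the High School B Part of It RCT (no, yes) will also be considered for inclusion in the adjusted model". No criterion is given, and the year contrasts are not separated from the vaccinated v unvaccinated contrasts. Unadjusted and adjusted analyses are both run, "with primary conclusions to be based on the results of adjusted analyses". Alcohol was added because it mattered "for disease-causing carriage in a preliminary analysis of 2018 School Leaver data".

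The protocol summary identifies Phase 1 with the school immunisation program. Protocol 2.2 says the pilot helps to validate Phase 1 laboratory work, and 6.1.1 says of the freezing comparison: "This will assist in validating laboratory procedures for the RCT study". Phase 1 is therefore the RCT.

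SAP 4.1 tabulates "Participation in the High School B Part of It Meningococcal Study" for 2018 and 2019, and MenB vaccine status beside it.

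**The concern.** The fixed covariates are behaviours, symptoms and ethnicity. RCT participation is different, because it lies between calendar year and vaccination. If more of the 2019 cohort had been in the RCT, and coverage rose for that reason, conditioning on participation removes exactly that rise. The adjusted odds ratio decides the conclusion, so one optional variable could separate the planned fall from no change.

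Participation is also a recruitment route. Protocol 4.1 contacts former participants, and 5.3 writes separately to Group B year 12 students. If the sampled mix differs by year for that reason, adjusting is the safer choice. The two models answer different questions, and the SAP does not say which one leads. Because 2018 carriage data had already been examined, the open choice also invites the suspicion that it was made to suit the result.

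**Working it through.** **The plan's own figure.** Inputs from SAP 5: 8% in 2018, 20% relative reduction (6.4%), two-sided 0.05, power 80%. With pooled variance and mean prevalence 0.072:

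n = [1.96·√(2·0.072·0.928) + 0.8416·√(0.08·0.92 + 0.064·0.936)]² / 0.016² = 4,096 per year.

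This matches. The planned odds ratio (2018 v 2019) is (0.08/0.92)/(0.064/0.936) = 1.272.

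**Effect of the participation term.** From the documents: 8% carriage in 2018, 4,096 per year, and about two thirds immunised (protocol 2.2), used here for 2019. Assumed, because the documents are silent: the 2018 coverage c₁, the vaccine effect e on carriage, participation shares by year, no vaccination outside the RCT and no indirect effect. Carriage is p₀ if unvaccinated and p₀(1 − e) if vaccinated.

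A 20% fall requires 1 − (2/3)e = 0.8(1 − c₁e), so e = 0.2/(2/3 − 0.8c₁). For c₁ = 0, 1/6, 1/4, 1/3, 1/2 this gives e = 0.30, 0.375, 0.43, 0.50, 0.75. Logistic models were fitted to expected counts with year alone, then with year and participation (two-sided Wald test):

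| Why coverage rose | OR without term (power) | OR with term (power) |
|---|---|---|
| Only participation rose; all participants vaccinated | 1.27 (80%) | 1.00 (5%) |
| Participation covers about half the rise | 1.27 (80%) | 1.14 to 1.20 (33% to 51%) |
| Participation 2/3 in both years; later doses among participants | 1.27 (80%) | 1.27 to 1.28 (80% to 81%) |

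Example at c₁ = 1/3: e = 0.50 and p₀ = 0.08/(1 − 0.5/3) = 0.096. In the first row participants carry at 0.048 and non-participants at 0.096 in both years, so the odds ratio within strata is 1.00. In the third row participants fall from 0.096 × 0.75 = 0.072 to 0.048, and the adjusted model keeps the whole fall.

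**Smaller vaccine effects.** With coverage 1/3 then 2/3 and e = 0.1, 0.2, 0.3, the odds ratio without the term is 1.04, 1.08, 1.14. With the term it lies between 1.00 and that value.

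**Coverage as protocol 2.2 states it.** Two thirds are expected to be immunised for both 2018 and 2019. With equal participation as well, both models give 1.00.

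**Only recruitment differs.** Take participants as 3/4 of the 2018 sample and 1/2 of the 2019 sample, all vaccinated, with e = 0.3. Then p₀ = 0.08/(1 − 0.225) = 0.1032 and 2019 carriage is 0.1032 × 0.85 = 0.0877. Without the term the odds ratio is (0.08/0.92)/(0.0877/0.9123) = 0.90. With it, 1.00. Here the term removes a false result.

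**Indirect effects.** Let participation equal vaccination (33% then 67%), with base carriage 8% and vaccinated carriage 0.6 times unvaccinated. Add a 10% indirect fall in everyone in 2019. The odds ratio is 1/0.746 = 1.34 without the term and 1/0.894 = 1.12 with it. The indirect part survives adjustment.

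**The case for a change.** The strongest case for a change is that this is the only primary analysis, its covariate list is incomplete, the adjusted result governs, and a yes or no would cost one sentence. The unadjusted analysis is not a full substitute, because it drops the other covariates too. All of that stands as a description of the text, and a prespecified choice would be tidier.

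The rest is weaker. The full swing from 1.27 to 1.00 needs participation to equal vaccination and the participant share to change between years. The documents point away from the first condition. SAP 6.1 counts RCT participants as vaccinated only after two doses at least a month before the swab, and it provides for checking vaccination in non-participants. Protocol 5.3 describes Group B participants with both doses still due. If that explains lower 2018 coverage, the rise falls within participants and adjustment costs nothing. The full swing also requires vaccine effects of 30% to 75% on all six genogroups together, chosen to produce the planned fall.

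On timing, the documents disclose a look at 2018 data only, and cite it for alcohol. One year's data cannot show which way the term would move a 2018 v 2019 odds ratio. Nothing says that 2019 carriage had been seen.

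The Unsure category for participation in SAP 4.1 does not fit a no/yes covariate, but the RCT database that SAP 6.1 already uses can resolve it.

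**Conclusion.** No change is needed. The open wording leaves an ordinary modelling decision to the analysts, and the trade-off is real on both sides. Leaving participation out keeps the whole direct programme effect but lets recruitment mix bias the year contrast (0.90 against 1.00 in the example). Putting it in corrects the mix but can remove direct effect (1.27 down to anything from 1.00 to no loss). The documents do not settle which matters more, so prescribing one model would replace one defensible choice with another. No rule or figure in the plan is wrong: 4,096 per year does give "80% power to detect a 20% relative reduction in carriage prevalence between 2018 and 2019". The unadjusted result and the by-year tables of participation and MenB status let a reader judge the part played by a changed participant share. These sizes rest on assumed participation shares, 2018 coverage and vaccine effects, so they show what could happen and are not estimates of what will.

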6.3 Multiple comparisons and multiplicity

No adjustment will be made for multiple comparisons, as there is only a single primary outcome and the multiple secondary outcomes are of less importance and will be considered exploratory.

6.4 Primary Outcome

6.4.1 Carriage prevalence of disease causing genogroups of *N. meningitidis* (A, B, C, W, X, Y) in school leavers in 2018 compared to 2019

Outcome: Binary outcome based on the presence of at least one disease-causing genogroup of *N. meningitidis* (A, B, C, W, X, Y) by polymerase chain reaction (PCR).

Effect: Odds ratio for disease-causing genogroups of *N. meningitidis* (2018 vs 2019).

Analysis: Test for a difference using logistic regression. Adjustment will be conducted as described in 6.2.

6.5 Secondary Outcomes

6.5.1 Carriage prevalence of all genogroups of *N. meningitidis* in school leavers in 2018 compared to 2019

Outcome: Binary outcome based on the presence of any *N. meningitidis*

(groupable or non-groupable) by PCR.

Effect: Odds ratio for all genogroups of *N. meningitidis* (2018 vs 2019).

Analysis: Test for a difference using logistic regression. Adjustment will be conducted as described in 6.2.

6.5.2 Carriage prevalence of each individual group of *N. meningitidis* (A, B, C, W, X, Y, and non-groupable) in school leavers in 2018 compared to 2019

Outcome: Binary outcomes (one for each group) based on the presence of specific meningococcal DNA by PCR for genogroups A, B, C, W, X, Y and non-groupable.

Effect: Odds ratio for *N. meningitidis* carriage for each genogroup (2018 vs 2019).

Analysis: Test for a difference using logistic regression. Adjustment will be conducted as described in 6.2.

6.5.3 Carriage prevalence of disease-causing genogroups of *N. meningitidis* (A, B, C, W, X, Y) in vaccinated compared to unvaccinated school leavers

Outcome: Binary outcome based on the presence of at least one disease-causing genogroup of *N. meningitidis* (A, B, C, W, X, Y) by polymerase chain reaction (PCR).

Effect: Odds ratio for disease-causing genogroups of *N. meningitidis* (4CMenB Vaccinated vs 4CMenB Unvaccinated).

Analysis: Test for a difference using logistic regression. Adjustment will be conducted as described in 6.2.

6.5.4 Carriage prevalence of all *N. meningitidis* in vaccinated compared to unvaccinated school leavers

Outcome: Binary outcome based on the presence of any *N. meningitidis* (groupable or non-groupable) by polymerase chain reaction (PCR).

Effect: Odds ratio for any *N. meningitidis* (4CMenB Vaccinated vs 4CMenB Unvaccinated).

Analysis: Test for a difference using logistic regression. Adjustment will be conducted as described in 6.2.

6.5.5 Carriage prevalence of each individual group of *N. meningitidis* (A, B, C, W, X, Y, and non-groupable) in vaccinated compared to unvaccinated school leavers

Outcome: Binary outcome (one for each group) based on the presence of *N. meningitidis* (groupable and non-groupable) by PCR.

Effect: Odds ratio for each individual genogroup of *N. meningitidis* (4CMenB Vaccinated vs 4CMenB Unvaccinated).

Analysis: Test for a difference using logistic regression. Adjustment will be conducted as described in 6.2.

6.5.6 Carriage prevalence of disease-causing genogroups of *N. meningitidis* (A, B, C, W, X, Y) among vaccinated school leavers by timing of vaccination

Outcome: Binary outcome based on the presence of at least one disease-causing genogroup of *N. meningitidis* (A, B, C, W, X, Y) by polymerase chain reaction (PCR).

Effect: Odds ratio for disease-causing genogroups of *N. meningitidis* for each additional month since vaccination (based on receipt of the 2nd dose).

Analysis: Test for an association using logistic regression, with months since vaccination treated as a continuous variable. Adjustment will be conducted as described in 6.2.

6.5.7 Carriage prevalence of all genogroups of *N. meningitidis* among vaccinated school leavers by timing of vaccination

Outcome: Binary outcome based on the presence of any *N. meningitidis* (groupable or non-groupable) by polymerase chain reaction (PCR).

Effect: Odds ratio for any *N. meningitidis* for each additional month since vaccination (based on receipt of the 2nd dose).

Analysis: Test for an association using logistic regression, with months since vaccination treated as a continuous variable. Adjustment will be conducted as described in 6.2.

7. STATISTICAL METHODS FOR ADDITIONAL STUDY OBJECTIVES

Additional objectives of the study, which do not involve group comparisons, are to:

1. Identify characteristics associated with carriage of any *N. meningitidis* (groupable and non-groupable) in South Australian school leavers.
2. Identify characteristics associated with carriage prevalence of at least one disease-causing genogroup of *N. meningitidis* (A, B, C, W, X, Y) in South Australian school leavers.

For these objectives, characteristics associated with carriage of *N. meningitidis* will be identified using logistic regression models, with effects described as odds ratios with 95% confidence intervals. Both univariable and multivariable logistic regression models will be fitted.

